10.3. Appendix 3: Liver Safety – Study Treatment Restart or Rechallenge Guidelines

10.3.1. VSLC Guidelines for Drug Restart or Rechallenge after stop for Liver criteria

Drug Rechallenge refers to resuming study treatment following drug induced liver injury (DILI). Because of the risks associated with rechallenge after DILI (see Drug Rechallenge Background below) this should only be considered for a participant for whom there is compelling evidence of benefit from a critical or life-saving medicine, there is no alternative approved medicine available, and a benefit:risk assessment of rechallenge is considered to be favorable (Table 13, Figure 5).

Drug Restart refers to resuming study treatment following liver events meeting stopping criteria **in which there is a clear underlying cause (other than DILI) of the liver event (e.g., biliary obstruction, pancreatic events, hypotension, acute viral hepatitis)**. Furthermore, there should be no evidence of alcoholic hepatitis or hypersensitivity, and the drug should not be associated with HLA markers of liver injury. (Table 14; Figure 6). **As this determination can be difficult, for the purpose of these guidelines, cases should be treated as rechallenges if there is any reasonable likelihood that the liver event is related to study drug. Restarts should be limited to cases in which there is clear evidence that the underlying cause of the liver event is not related to study drug.**

DRUG RECHALLENGE

Background: Following drug-induced liver injury, drug rechallenge is associated with a 13% mortality across all drugs in prospective studies [Andrade, 2009]. Clinical outcomes vary by drug, with nearly 50% fatality with halothane re-administered within one month of initial injury. However, some drugs seldom result in recurrent liver injury or fatality.

Risk factors for a fatal drug rechallenge outcome include:

[figure not shown]
- hypersensitivity [Andrade, 2009] with initial liver injury (e.g. fever, rash, eosinophilia)
- jaundice or bilirubin >2xULN with initial liver injury (direct bilirubin >35% of total)
- participant currently exhibits severe liver injury defined by: ALT≥3xULN, bilirubin ≥2xULN (direct bilirubin >35% of total), or INR≥1.5
- prior serious adverse event or fatality has earlier been observed with drug rechallenge [Papay, 2009; Hunt, 2010]
- evidence of drug-related nonclinical liability (e.g. reactive metabolites; mitochondrial impairment [Hunt, 2010])

10.3.2. VSLC Decision Process for Drug Rechallenge Approval or Disapproval

- Principal Investigator (PI) requests consideration of drug rechallenge for a participant receiving compelling benefit from a critical or life-saving drug, who exhibits liver chemistry elevation meeting participant stopping criteria in relation to DILI, with no alternative treatment
- By definition treatment naïve participants will only be considered for rechallenge if they were infected with a multi-resistant virus.
- Medical Monitor and Global Clinical Safety and Pharmacovigilance (GCSP) Physician review the participant's rechallenge risk factors (consultation with the Hepatotoxicity Panel is available) and complete checklist (Table 13).
- The local operating company (LOC) medical directors (ViiV and/or GSK where applicable) should be informed that study drug rechallenge is under consideration and of the final decision, whether or not to proceed.
- The Medical Monitor and GCSP Physician are accountable to review and agree on the following prior to preparing request for rechallenge documentation for presentation to VSLC:
 - Compelling benefit of the investigational product (IP) for this participant and no alternative therapy
 - *must present source data defining the patient's current resistance profile with documented evidence of extensive drug resistance and previous drug history*
- Relative benefit-risk of drug rechallenge, with consideration of the following high risk factors:
 - Initial liver injury event included: fever, rash, eosinophilia, or bilirubin $\geq 2xULN$ (or direct bilirubin $>35\%$ of total, if available)
 - Participant currently exhibits severe liver injury defined by: ALT $>3xULN$, bilirubin $>2xULN$ (direct bilirubin $>35\%$ of total, if available), or INR >1.5
 - SAE or fatality has earlier been observed with IP rechallenge
 - IP is associated with known nonclinical hepatic liability/ injury
- Relevant physicians (listed below) must review and agree on action to be taken regarding request for drug rechallenge:
 - Safety Review Team Leader, Safety Development Leader, or Senior Safety Physician
 - Medicines Development Leader (MDL) and Project Physician Leader (PPL)
- Request is taken to full VSLC for final decision

Table 13 Checklist for drug rechallenge for critical medicine (Following drug-induced liver injury, drug rechallenge is associated with 13% mortality across all drugs in prospective studies)

	Yes	No
Compelling benefit of IP for this participant and no alternative therapy. Provide brief explanation:		
Relative benefit-risk favorable for drug rechallenge, after considering the following high risk factors:		
Initial liver injury event included:		
fever, rash, eosinophilia, or hypersensitivity		
bilirubin \geq 2xULN (direct bilirubin >35% of total)		
Participant currently exhibits ALT >3xULN, bilirubin >2xULN (direct bilirubin >35% of total, if available), or INR>1.5		
SAE or fatality has earlier been observed with IP rechallenge If yes, please provide brief explanation:		
IP associated with known nonclinical hepatic liability/ injury		
Source data defining the patient's current resistance profile		
Previous drug history		

Figure 5 VSLC process for drug rechallenge approval or disapproval**DRUG RESTART**

“Drug restart” can be approved by the VSLC for **transient, defined non-drug-induced** liver injury if no evidence of:

- immunoallergic injury /HLA association with injury
- alcoholic hepatitis

[figure not shown]
Study drug must be held while labs and evaluation are completed to assess diagnosis.

10.3.3. VSLC Decision Process for Drug Restart Approval or Disapproval

- Principal Investigator (PI) requests consideration of drug re-initiation for a participant stable or improving on IP, who exhibits liver chemistry elevation meeting participant stopping criteria, which is transient, non-drug-related, and liver chemistries have improved to normal or are within 1.5x baseline and ALT < 5xULN.
- GSK Medical Monitor and GCSP Physician to review the participant's diagnosis restart risk factors (Hepatotoxicity Panel consultation is available) and complete checklist (Table 14).
 - *must present source data defining the patient's current resistance profile with documented evidence of extensive drug resistance and previous drug history.*
- The local operating company (LOC) medical director should be informed that study drug restart is under consideration and of the final decision, whether or not to proceed.
- Relevant physicians (listed below) must review and agree on action to be taken regarding request for drug restart:
- Safety Review Team Leader, Safety Development Leader, or Senior Safety Physician
- MDL and PPL
- Request is taken to VSLC for final decision

Table 14 Checklist for Phase III drug restart after well-explained liver injury (e.g. biliary, pancreatic, hypotensive events, congestive heart failure (CHF), acute viral hepatitis), and improvement of liver chemistry to normal or $\leq 1.5x$ baseline & ALT < 5xULN

	Yes	No
Is participant stable or improving on IP?		
Do not restart if the following risk factors at initial liver injury:		
fever, rash, eosinophilia, or hypersensitivity		
drug-induced liver injury		
alcoholic hepatitis (AST > ALT, typically < 10xULN)		
IP has an HLA genetic marker associated with liver injury (e.g. lapatinib, abacavir, amoxicillin/clavulanate)		
Source data defining the patients current resistance profile		
Previous drug history		

Figure 6 VSLC process for drug restart approval or disapproval

10.3.4. Medical monitor, GCSP Physician and PI actions for Restart or Rechallenge following VSLC decision

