1.5. Schedule of Activities (SoA)

There are additional PK assessments for any pregnant participants who are remaining in the study. See [Appendix 8](#)

Table 3 Schedule of Activities for Patient Study Participants (CAB LA + RPV LA Monthly Administration)

Procedures	Screening ^a	Intervention Period												WD ^o	
		Day 1	Month 1	Month 2	Month 3	Month 4	Month 5	Month 6	Month 7	Month 8	Month 9	Month 10 ^c	Month 11 ^c		Month 12 ^c
Written Informed Consent ^b	X														
Demography	X														
Eligibility Verification	X														
Physical Exam	X														
Medical History	X														
Center for Disease Control and Prevention (CDC) Classification	X														
Randomization for interviews		X													
Rapid Plasma Reagin (RPR)	X														

Procedures	Screening ^a	Intervention Period												WD ^o	
		Day 1	Month 1	Month 2	Month 3	Month 4	Month 5	Month 6	Month 7	Month 8	Month 9	Month 10 ^c	Month 11 ^c		Month 12 ^c
Symptom Directed Physical Exam and Medical Assessment ^d	X	X	X	X		X		X		X		X		X	X
Injection site reaction (ISR) assessment			X	X	X	X	X	X	X	X	X	X	X	X	X
Vital Signs (temperature, blood pressure [BP], heart rate [HR]) ^e	X	X	X	X		X		X			X			X	X
Weight, Height & body mass index (BMI) ^f	X	X	X					X						X	X
HIV Associated Conditions, AE and serious adverse event (SAE) Assessments & Con Meds	X	X	X	X		X		X		X		X		X	X
12-Lead ECG ^g	X														X

Procedures	Screening ^a	Intervention Period												WD ^o	
		Day 1	Month 1	Month 2	Month 3	Month 4	Month 5	Month 6	Month 7	Month 8	Month 9	Month 10 ^c	Month 11 ^c		Month 12 ^c
Clinical and Hematology			X	X		X		X			X			X	X
Pregnancy Testing (U)rine or (S)erum ^h	U	U	U	U	U	U	U	U	U	U	U	U	U	U	U
HIV-1 RNA	X	X	X	X		X		X		X		X		X	X
Plasma sample for storage ^{i,j}		X	X	X		X		X		X		X		X	X
CD4+cell counts	X	X	X	X		X		X			X			X	X
Urinalysis	X														X
Glucose	X														
Prothrombin time (PT)/ partial thromboplastin time (PTT)/ international normalized ratio (INR)	X														X
Oral study product dispensation		X													

Procedures	Screening ^a	Intervention Period													WD ^o
		Day 1	Month 1	Month 2	Month 3	Month 4	Month 5	Month 6	Month 7	Month 8	Month 9	Month 10 ^c	Month 11 ^c	Month 12 ^c	
LA study product administration ^k			X ⁿ	X	X	X	X	X	X	X	X	X	X	X	
Participant Visit Reminder Contact	X	X	X	X	X	X	X	X	X	X	X	X	X	X	
Participant Contact Detail Confirmation	X	X	X	X	X	X	X	X	X	X	X	X	X	X	
Record study visit length ^l			X				X						X		

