Acidosis	NA	pH \geq 7.3 to $<$ LLN	pH $<$ 7.3 without life-threatening consequences	pH $<$ 7.3 with life-threatening consequences
Albumin, Low (g/dL; g/L)	3.0 to $<$ LLN 30 to $<$ LLN	\geq 2.0 to $<$ 3.0 \geq 20 to $<$ 30	$<$ 2.0 $<$ 20	NA
Alkaline Phosphatase, High	1.25 to $<$ 2.5 x ULN	2.5 to $<$ 5.0 x ULN	5.0 to $<$ 10.0 x ULN	\geq 10.0 x ULN
Alkalosis	NA	pH $>$ ULN to \leq 7.5	pH $>$ 7.5 without life-threatening consequences	pH $>$ 7.5 with life-threatening consequences
ALT or SGPT, High Report only one	1.25 to $<$ 2.5 x ULN	2.5 to $<$ 5.0 x ULN	5.0 to $<$ 10.0 x ULN	\geq 10.0 x ULN
Amylase (Pancreatic) or Amylase (Total), High Report only one	1.1 to $<$ 1.5 x ULN	1.5 to $<$ 3.0 x ULN	3.0 to $<$ 5.0 x ULN	\geq 5.0 x ULN
AST or SGOT, High Report only one	1.25 to $<$ 2.5 x ULN	2.5 to $<$ 5.0 x ULN	5.0 to $<$ 10.0 x ULN	\geq 10.0 x ULN
Bicarbonate, Low (mEq/L; mmol/L)	16.0 to $<$ LLN 16.0 to $<$ LLN	11.0 to $<$ 16.0 11.0 to $<$ 16.0	8.0 to $<$ 11.0 8.0 to $<$ 11.0	$<$ 8.0 $<$ 8.0
Bilirubin Direct Bilirubin¹³, High > 28 days of age	NA	NA	$>$ ULN with other signs and symptoms of hepatotoxicity.	$>$ ULN with life-threatening consequences (e.g., signs and symptoms of liver failure)
\leq 28 days of age	ULN to \leq 1 mg/dL	$>$ 1 to \leq 1.5 mg/dL	$>$ 1.5 to \leq 2 mg/dL	$>$ 2 mg/dL
Total Bilirubin, High > 28 days of age	1.1 to $<$ 1.6 x ULN	1.6 to $<$ 2.6 x ULN	2.6 to $<$ 5.0 x ULN with other signs and symptoms of hepatotoxicity.	\geq 5.0 x ULN with life-threatening consequences (e.g., signs and symptoms of liver failure).
\leq 28 days of age	See Appendix A. Total Bilirubin for Term and Preterm Neonates	See Appendix A. Total Bilirubin for Term and Preterm Neonates	See Appendix A. Total Bilirubin for Term and Preterm Neonates	See Appendix A. Total Bilirubin for Term and Preterm Neonates

*Reminder: An asymptomatic abnormal laboratory finding without an accompanying AE should not be reported to DAIDS in an expedited time frame unless it meets protocol-specific reporting requirements.

¹³ Direct bilirubin $>$ 1.5 mg/dL in a participant $<$ 28 days of age should be graded as grade 2, if $<$ 10% of the total bilirubin.

Chemistries

PARAMETER	GRADE 1 MILD	GRADE 2 MODERATE	GRADE 3 SEVERE	GRADE 4 POTENTIALLY LIFE- THREATENING
Calcium, High (mg/dL; mmol/L) ≥ 7 days of age	10.6 to < 11.5 2.65 to < 2.88	11.5 to < 12.5 2.88 to < 3.13	12.5 to < 13.5 3.13 to < 3.38	≥ 13.5 ≥ 3.38

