10.6.2. Liver Chemistry Stopping and Follow-up Criteria

Liver chemistry threshold stopping criteria have been designed to assure participant safety and to evaluate liver event etiology during administration of study drug and the follow-up phase (See also Section 10.3, [Appendix 3](#)). All Phase 3 participants who meet liver stopping criteria will be adjudicated by the ViiV Safety and Labelling Committee (VSLC) – resulting in a case summary, adjudication, and management plan. The VSLC contains an external expert hepatologist, familiar with both DILI and cabotegravir, who will participate in this review. This committee meets on a 3-weekly basis, and can be convened on an ad hoc basis as needed.

Drug Restart Following Transient Resolving Liver Events Not Related to Study Drug

Approval by VSLC for drug restart can be considered where:

Liver chemistries have a clear underlying cause (e.g., biliary obstruction, hypotension, and liver chemistries have improved to normal or are within $1.5 \times$ baseline and $ALT < 3 \times ULN$). Ethics Committee or IRB approval of drug restart must be obtained, as required.

If restart of drug is approved by VSLC in writing, the participant must be provided with a clear description of the possible benefits and risks of drug administration, including the possibility of recurrent, more severe liver injury or death.

The participant must also provide signed informed consent specifically for the restart. Documentation of informed consent must be recorded in the study chart.

Study drug must be administered at the dose specified by VSLC.

Participants approved by VSLC for restarting study drug must return to the clinic once a week for liver chemistry tests for a minimum of one month and thereafter for as long as clinically indicated and then laboratory monitoring may resume as per protocol. If protocol defined stopping criteria for liver chemistry elevations are met, study drug must be stopped.

Refer to Section 10.2, Appendix 2, U.S. Department of Health and Human Services, National Institutes of Health, National Institute of Allergy and Infectious Diseases, Division of AIDS. Division of AIDS (DAIDS) Table for Grading the Severity of Adult and Pediatric Adverse Events, Version 2.1. [March 2017]. Available from: <https://rsc.tech-res.com/docs/default-source/safety/daids-ae-grading-table-mar2017.pdf>

Refer to Section 10.3.3: Liver Safety – Study Treatment Restart Guidelines for further details.

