10.6.3. Grade 1 or Grade 2 Toxicity/Adverse Event

Participants who develop a Grade 1 or Grade 2 AE or toxicity may continue IP at the discretion of the Investigator. (NOTE: See Section 10.6 Appendix 6, Specific Toxicities/Adverse Event Management” for exceptions to this guideline). Participants who choose to withdraw from study due to a Grade 1 or 2 AE should have study withdrawal and follow-up evaluations completed.

Participants who develop ALT ≥ 3 times ULN while on study must consult with Medical Monitor prior to initiation or continuation of CAB LA and RPV LA.

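### The liver-restart rule carries two ALT limits for the same committee decision: below 5xULN in Section 10.3.3 and Table 14, below 3xULN in Section 10.6.2

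*Protocol*

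**What the plan says.** Section 10.3.3 (Appendix 3) describes how a restart request reaches the VSLC. The investigator may ask for study drug to be resumed in a participant whose liver event was transient and unrelated to study drug, once chemistries are normal or "within 1.5x baseline and ALT < 5xULN". Table 14, the checklist for that request, gives the same upper bound in its title: "baseline & ALT < 5xULN". The section ends with the VSLC taking the final decision.

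Section 10.6.2 (Appendix 6) covers the same situation: "Approval by VSLC for drug restart can be considered where" the event has a clear underlying cause and chemistries are normal or within 1.5 times baseline. Here, however, the bound reads "baseline and $ALT < 3" times ULN (the dollar sign comes from text conversion). The section closes by sending the reader to Section 10.3.3, "Study Treatment Restart Guidelines for further details".

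Section 10.6.3 uses 3xULN as an action point. Participants whose ALT reaches at least 3 "times ULN while on study must consult with Medical Monitor prior to initiation or continuation of CAB LA and RPV LA".

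**The concern.** Both sections concern the same committee, the same type of event and the same 1.5-times-baseline condition. Only the ALT ceiling differs. Both are current text and each is in use: Section 7 points to Section 10.6.2 for the liver criteria, and Table 14 is what the medical monitor and safety physician complete. The cross-reference leads from one limit to the other without settling which applies.

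At stake is whether a participant may resume study drug after a liver event. Someone who has received at least one long-acting dose and does not resume goes on to HAART and 52 weeks of follow-up (Section 7.1). The investigator needs to know when a request is admissible, and the committee needs to know which written limit it is applying. No objective, endpoint or analysis depends on the answer.

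**Working it through.** The plan has no figure to reproduce here. The check is when the two rules give different answers.

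Inputs, all in multiples of ULN, with b = baseline ALT and a = current ALT:
- Section 10.3.3 and Table 14: a ≤ 1.5b and a < 5.
- Section 10.6.2: a ≤ 1.5b and a < 3.
- Exclusion 22 (Section 5.2): ALT ≥5xULN is excluded, as is ALT ≥3xULN together with bilirubin ≥1.5xULN (more than 35% direct).

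A normal ALT satisfies both rules, so only the baseline route matters.

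**Where they conflict.** The rules disagree when 3 ≤ a < 5 and a ≤ 1.5b, that is, when b ≥ a/1.5. The smallest such baseline is 3/1.5 = 2.0. The whole interval up to 5 is in dispute once b exceeds 5/1.5 = 3.33.

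| Baseline ALT | 1.5 × baseline | ALT values in dispute |
|---|---|---|
| 1.9 | 2.85 | none |
| 2.0 | 3.0 | 3.0 only |
| 2.4 | 3.6 | 3.0 to 3.6 |
| 3.0 | 4.5 | 3.0 to 4.5 |
| 3.34 or more | 5.01 or more | 3.0 to below 5.0 |

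**Example.** With b = 2.4 and a = 3.5, a/b = 3.5/2.4 = 1.46, which is within 1.5. Since 3.5 < 5, the request passes Section 10.3.3 and Table 14. Since 3.5 ≥ 3, it fails Section 10.6.2.

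**A further consequence.** If b is 3.0 or more, a full return to baseline (a = b) still fails Section 10.6.2, while any b below 5 passes Section 10.3.3.

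**Can such baselines occur?** Yes. Exclusion 22 does not bar ALT from 2 to below 3xULN, and it bars 3 to below 5xULN only with raised bilirubin. All these baselines are at least Grade 1 in the Appendix 2 row "ALT or SGPT, High", which starts at 1.25xULN. The participants would therefore already have been discussed with the medical monitor under Section 5.2.1.

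**The case against.** **The two limits could be two gates.** Section 10.3.3 begins with when the investigator may request restart, and Section 10.6.2 says when the VSLC may consider approving it. A request gate below 5xULN followed by an approval gate below 3xULN would be coherent, and the stricter limit would bind. The reading is strained. Section 10.3.3 carries the process through to the committee's final decision without mentioning a second threshold, and Section 10.6.2 defers to it for detail.

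**The disputed range may be empty.** This largely stands. The study expects at most about 135 patients. The participant needs a baseline ALT of at least 2xULN and a resolving liver event with a non-drug cause. Section 10.3.3 also asks for documented evidence of extensive drug resistance, while entry rules out regimen switches for treatment failure and major integrase or NNRTI mutations other than K103N.

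**Safeguards surround every case.** This also stands. A reader might infer that the higher figure lets participants restart unsafely. The documents do not support that, because neither limit compels a restart. Each case needs VSLC adjudication with an external hepatologist, written approval, specific consent and weekly liver tests for at least a month. These reduce the risk but do not say which limit applies.

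**A wider reading to avoid.** A reader might infer from Table 3 that baseline ALT is never drawn, since the row "Clinical and Hematology" shows no mark at Screening or Day 1, or that hepatitis B testing was left out because Table 3 and Section 8.4.5 do not list it. Neither is established. The row label appears damaged in the copy reviewed (Table 5 includes the word chemistry), so marks may have been lost too. Sections 2.3.1, 5.1, 8.1 and 8.2.1 call for the screening and Day 1 laboratory work, and Exclusion 9 names the hepatitis B tests.

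**Conclusion.** The inconsistency is real and wrong as written: one safety decision has two ALT limits, and the text does not rank them. Its reach is narrow. The answers differ only for baseline ALT of at least 2xULN with current ALT of 3 to below 5xULN and within 1.5 times baseline; below a baseline of 2xULN the rules agree. This takes the baseline condition as inclusive, as Table 14 writes it. The documents give no baseline ALT distribution, so no expected count can be stated, but few participants, if any, should be affected. The conclusion rests on the plain wording of Sections 10.3.3 and 10.6.2 and not on any table layout. The Table 3 marks and the hepatitis B listing form no part of it.

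**What to change.** State a single ALT restart limit in Section 10.3.3, the title of Table 14 and Section 10.6.2. Use below 3xULN, which fits the consultation point in Section 10.6.3, unless the VSLC documents why below 5xULN is preferred. One consideration for the committee is that a 3xULN ceiling shuts out a participant whose own baseline is 3xULN or higher, even after full recovery to that level.

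The cost is a wording correction in three places, by amendment or note to file, with no new procedures or data. It remains worth making for anyone still receiving study drug. While the text is open, the sponsor could check the original Table 3 row for its Screening and Day 1 marks; that is a check, not a correction this review can require.

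### The liver restart procedure demands proof of extensive drug resistance that belongs to rechallenge, and it carries two different ALT limits (<5×ULN and <3×ULN)

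*Protocol*

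**What the plan says.** Protocol Section 10.3.1 separates two routes back to study drug after a liver stop.

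- **Rechallenge** follows drug-induced liver injury. It is reserved for participants with compelling benefit for whom "there is no alternative approved medicine available".
- **Restart** applies where "there is a clear underlying cause (other than DILI) of the liver event". Its further bars are alcoholic hepatitis, hypersensitivity and an HLA association with liver injury.

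Section 10.3.2 (rechallenge) requires agreement on "Compelling benefit of the investigational product (IP) for this participant and no alternative therapy". It adds that treatment-naive participants "will only be considered for rechallenge if they were infected with a multi-resistant virus". Directly under the no-alternative item it places the demand for documented extensive resistance.

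Section 10.3.3 (restart) repeats that demand in the same words. Under the Medical Monitor and safety physician review, they "must present source data defining the patient's current resistance profile with documented evidence of extensive drug resistance and previous drug history". Table 14, the restart checklist, asks only for source data on the resistance profile and for previous drug history.

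On recovery, Section 10.3.3 says that "liver chemistries have improved to normal or are within 1.5x baseline and ALT < 5xULN", and the Table 14 title gives the same ALT limit. Section 10.6.2 describes the same VSLC restart decision with the same 1.5×baseline rule but with ALT below 3×ULN. It then refers the reader to Section 10.3.3 for details.

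**The concern.** The resistance line has a purpose in rechallenge, because extensive resistance is how one shows that no other regimen would work. Restart never asks whether an alternative exists. It asks whether the event had another cause and has resolved. Carried into Section 10.3.3, the line adds a mandatory item that the restart definition does not support and that this population can hardly supply. The protocol does not say whether a missing item is waived or ends the request.

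The route is relevant in this programme. Section 2.3.1 reports that transaminitis on cabotegravir was mostly explained by acute hepatitis C or other systemic infection, and Section 10.3.1 names acute viral hepatitis as a restart cause. Section 7 makes discontinuation mandatory only where stopping criteria are met and no compelling alternate cause is found. A participant who has had an injection and does not restart goes to other antiretroviral therapy and 52 weeks of follow-up.

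The ALT mismatch is a separate point. One safety decision has two numerical thresholds, with no rule on which prevails.

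**Working it through.** **Resistance demand: the texts side by side**

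| Place | No-alternative test? | Resistance wording |
|---|---|---|
| 10.3.1, rechallenge | Yes | None |
| 10.3.2, rechallenge process | Yes | Profile, documented extensive resistance, drug history |
| Table 13, rechallenge checklist | Yes | Profile and drug history only |
| 10.3.1, restart | No | None |
| 10.3.3, restart process | No | Profile, documented extensive resistance, drug history |
| Table 14, restart checklist | No | Profile and drug history only |
| 10.6.2, restart conditions | No | None |

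Table 13 asks for "Source data defining the patient's current resistance profile" and also omits the word extensive. Its absence from Table 14 is therefore not in itself a contradiction. The fault is that the Section 10.3.3 line has no test to serve.

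**Can an enrolled participant meet it?**

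- Inclusion 2 rules out earlier regimen switches made for treatment failure.
- Exclusion 21 rules out any known major INI or NNRTI mutation on a historical test, except K103N.
- Inclusion 4 requires HIV-1 RNA <50 c/mL at Screening. This is weaker evidence, because it shows current suppression and not the absence of past resistance.
- NRTI and PI mutations are not named as exclusions.

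Documented extensive resistance is therefore improbable but not impossible.

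**ALT limits: where they differ**

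Let *b* be baseline ALT in multiples of ULN, and take normal as at most 1×ULN. Recovery to normal or within 1.5×baseline gives a ceiling of max(1, 1.5*b*).

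- Section 10.3.3 and Table 14: ALT ≤ max(1, 1.5*b*) and ALT < 5.
- Section 10.6.2: ALT ≤ max(1, 1.5*b*) and ALT < 3.

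The limit of 3 begins to bind when 1.5*b* = 3, that is *b* = 3/1.5 = 2.0. The limit of 5 begins to bind when *b* = 5/1.5 = 3.33.

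| Baseline *b* (×ULN) | 1.5*b* | Allowed by 10.3.3 | Allowed by 10.6.2 | In dispute |
|---|---|---|---|---|
| below 2.0 | below 3 | up to max(1, 1.5*b*) | the same | none |
| 2.5 | 3.75 | up to 3.75 | <3 | 3 to 3.75 |
| 3.0 | 4.5 | up to 4.5 | <3 | 3 to 4.5 |
| 3.33 and above | 5 or more | <5 | <3 | 3 to <5 |

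For full return to baseline, set ALT = *b*. Section 10.3.3 allows restart for *b* < 5 and Section 10.6.2 only for *b* < 3, so participants with 3 ≤ *b* < 5 are barred by Section 10.6.2 alone.

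Such baselines can enter the study. Exclusion 22 bars ALT ≥5×ULN, or ALT ≥3×ULN together with bilirubin ≥1.5×ULN and more than 35% direct.

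**The case against.** The strongest reply is that the resistance line is a dossier item and not an approval criterion. Sections 10.3.1 and 10.6.2 state when restart can be approved without mentioning resistance. Table 14 puts its outright bars under a do-not-restart heading and lists resistance data separately. Every request goes to the VSLC for a final decision, and nothing makes a missing item an automatic refusal. Figure 6, the restart flow, is not shown. All of this stands, and it means the line adds a condition without contradicting another statement. It does not remove a "must" that reviewers can seldom satisfy and for which no waiver is written.

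On ALT, the disputed cases are few and already watched:

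- Grade 1 or higher liver tests at Screening or Day 1 go to the Medical Monitor before long-acting dosing (Section 5.2.1).
- Anyone who develops ALT ≥3×ULN on study needs Medical Monitor consultation before dosing starts or continues (Sections 2.3.1 and 10.6.3).
- Restart also needs VSLC review with an external hepatologist, fresh consent and at least a month of weekly liver tests (Sections 10.3.6 and 10.6.2).

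One could also apply both limits and let the stricter bind, but the protocol does not say so. These safeguards reduce the consequence. They do not tell anyone which limit to use.

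Finally, the outcomes template in Section 10.3.6 is kept across studies, so the wording may be shared beyond this trial and not quite free to edit locally. That bears on the cost, not on whether the text is right.

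**Conclusion.** Both points hold, and both are minor. Section 10.3.3 carries a rechallenge condition that the restart definition does not support and that eligible participants can hardly meet. Read literally, it would hold up restarts that Sections 10.3.1 and 10.6.2 allow. Restart also has two ALT limits, which give different answers only for baseline ALT of 2×ULN or more and current ALT from 3 to <5×ULN within 1.5×baseline.

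The protocol gives no rate of liver stops, of resistance or of raised baseline ALT, so no number of affected participants is claimed. The first conclusion assumes that Figure 6 does not already settle the matter. The effect is on liver-safety management. The survey endpoints, sample size and analyses are not affected.

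**What to change.** In Section 10.3.3, delete the phrase requiring documented evidence of extensive drug resistance. Keep the request for "source data defining the patient's current resistance profile" and for previous drug history, which is what Table 14 asks for. Leave Section 10.3.2 as it is, and check Figure 6 for the same wording.

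Separately, state one restart ALT limit in Section 10.3.3, the Table 14 title and Section 10.6.2. The documents do not show which value was intended, so the VSLC should choose it with its hepatologist. If <3×ULN is chosen, say how participants with baseline ALT of 3 to <5×ULN are handled, since they could not restart even at their own baseline.

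The cost is one deleted phrase and one short committee decision, written the same way in three places at the next amendment. If the liver text is a shared template, the committee's agreement to a local change is also needed. No procedures are added for participants.
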